16.1.1 All TEAEs

Incidence of TEAEs and AEs along with the number of events, will be presented by SOC and PT. AEs occurred more than once within that SOC/ PT will be counted once in the summary tables (at least one occurrence). The SOCs will be presented by alphabetical order, and PTs by descending frequency within each SOC.

16.1.1.1 Severity

Severity is classed as mild/ moderate/ severe (increasing severity). TEAEs with a missing severity will be classified as severe.

16.1.1.2 Relationship to Study Device

Relationship, as indicated by the Investigator, is classed as "unrelated", "unlikely", "possibly", "probably" (increasing severity of relationship). A "related" TEAE is defined as a TEAE with a relationship as "unlikely", "possibly", "probably". TEAEs with a missing relationship will be regarded as related. For related TEAEs summaries of incidence rates (frequencies and percentages) by SOC and PT will be prepared together with number of events. In case of less than 5 events, a listing only will be provided.

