## 7.1.5. Relationship to treatment

For all events reported, the treating physician or other reporting health care provider will be asked to assess the relationship of the AE/SAEs to DryNites® (if relevant – see below) using the following definitions:

- Probable: A causal relationship is clinically/biologically highly plausible, and there is a correlation between the onset of the AE/SAE and administration of the treatment, and between withdrawal of treatment and resolution of the AE/SAE.
- Possible: A causal relationship is clinically/biologically plausible and there is a correlation between the onset of the AE/SAE and administration of the treatment.
- Unlikely: A causal relationship is improbable, and another documented cause of the AE/SAE is most plausible.
- Unrelated: A causal relationship can be definitively excluded, and another documented cause of the AE/SAE is most plausible.

An adverse device effect (ADE) is defined as an adverse event related to the use of an investigational medical device. This definition includes AEs resulting from insufficient or inadequate instructions for use, deployment, implantation, installation, or operation, or any malfunction of the investigational medical device, as well as any event resulting from use error or from intentional misuse of the investigational medical device.

An unanticipated serious adverse device effect (USADE) unanticipated serious adverse device effect (USADE) is a serious ADE, which by its nature, incidence, severity, or outcome has not been identified in the current version of the risk analysis report of the medical device.

Relationship to the use of DryNites® should be assessed for any AE occurring during the runin period and the intervention and extension periods in the control group (participants continuing the use of DryNites® absorbent pants); it is not applicable for the intervention group (participants discontinuing the use of absorbent pants).

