### 7.3. Procedures for Reporting Adverse Events to Sponsor Consumer Service

In addition to recording the event on the eCRF, all SAEs and non-serious AEs considered related to the use of DryNites® (ADEs) reported during follow-up must also be reported to the Sponsor Consumer Service for purposes of regulatory reporting, using the SAE form. Site personnel must complete and submit the appropriate SAE report form (available through the EDC system) within 24 hours of becoming aware of the event. All SAEs and non-serious AEs considered related to the use of DryNites® (ADEs) occurring after informed consent is signed and until study discontinuation should be reported in the EDC within 24 hours of learning of its occurrence. Once the SAE form is completed is modified in the EDC, this generates an immediate email notification of the SAE to the Sponsor.

In order to maintain compliance with the FDA, EMA and other international and national regulatory bodies, treating physicians may be further contacted by the Sponsor Safety department in order to collect additional information required to evaluate the potential event. AEs/SAEs will be reported to local and regional health authorities by the Sponsor, when appropriate, in accordance with applicable local and regional regulations. The participating

physician is responsible for maintaining compliance with any applicable site-specific requirements related to the reporting of SAEs or other safety information to the local IRB/IEC that approved the study.

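### The SAP counts AEs graded 'unlikely' as device-related, which does not fit the protocol's own definition of that grade

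*SAP*

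**What the plan says.** SAP 16.1.1.2 sets the rule: a related "TEAE is defined as a TEAE with a relationship as" *unlikely*, *possibly* or *probably*. It adds a rule for missing grades ("TEAEs with a missing relationship will be regarded as related") and a display threshold ("In case of less than 5 events, a listing only will be provided"). Related TEAEs are to be summarised by system organ class (SOC) and preferred term (PT), with event counts. No tabulation by relationship grade is planned.

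Protocol 7.1.5 defines the four grades. The two lower ones read "Unlikely: A causal relationship is improbable, and another documented cause of the AE/SAE is most plausible" and "Unrelated: A causal relationship can be definitively excluded, and another documented cause of the AE/SAE is most plausible". *Possible* and *probable* are the only grades described as plausible.

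The same section states: "An adverse device effect (ADE) is defined as an adverse event related to the use of an investigational medical device". Protocol 7.3 requires sites to report, within 24 hours, all SAEs and "non-serious AEs considered related to the use of DryNites", which it equates with ADEs. Protocol 5.4.4 asks for device-related TEAEs to be tabulated by group. None of these places says which grades count as related.

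Protocol 7.1.5 has relationship assessed in the run-in and, after randomisation, in the continuation arm only. For the discontinuation arm it is not applicable.

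**The concern.** An *unlikely* grade is a recorded judgement against causality: the investigator found the link improbable and had another documented cause. Under the SAP rule that event is reported as device-related. The summary table would then mix events the investigator considered plausible device effects with events attributed to something else. With no display by grade, a reader of the table could not separate them without going to the individual listings.

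The word related would also carry two meanings. A site following the wording of Protocol 7.1.5 would not naturally report an improbable event as an ADE, yet the SAP would count it. Neither SAP 16.1.1.2 nor the list of changes in SAP 4.3 gives a reason for the wider set.

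Protocol Section 2 says that the side-effects of DryNites have not been evaluated in any studies. A device-related count that means what its label says is therefore useful to readers of this trial.

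**Working it through.** There is no stated figure to reproduce. The documents give no expected AE rate, no share of events graded *unlikely* and no rash rate. The check compares the texts and then illustrates the size.

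**Step 1: the grades side by side**

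| Grade | Protocol 7.1.5, in substance | Related under SAP 16.1.1.2? |
|---|---|---|
| Probable | highly plausible; timing fits onset and withdrawal | yes |
| Possible | plausible; timing fits onset | yes |
| Unlikely | improbable; another documented cause most plausible | yes |
| Unrelated | definitively excluded; another documented cause most plausible | no |

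The protocol's change from plausible to not plausible lies between *possible* and *unlikely*. The SAP draws its line one grade lower.

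**Step 2: direction.** The SAP's related set contains the possible-or-probable set, so its count is equal or higher, never lower. It is strictly higher for events as soon as one TEAE is graded *unlikely*.

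**Step 3: where the excess falls.** After randomisation, recorded *unlikely* grades can arise only in the DryNites arm, because relationship is not assessed in the other arm. SAP 16.1 starts TEAEs at screening, and SAP 6.3 includes everyone exposed to DryNites for at least one night after consent. Run-in events in all enrolled children are therefore affected too. (This concerns recorded grades; the rule for missing grades is a separate matter.)

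**Step 4: size, on assumed counts.** Let *r* be the children with a possible or probable TEAE, *u* the children whose highest grade is *unlikely*, and *N* the denominator.

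- SAP rule: (r + u)/N
- Possible or probable only: r/N
- Excess: (r + u)/N − r/N = u/N

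N = 40 is the DryNites arm if about 120 are randomised 2:1 (120/3 = 40). N = 120 is all randomised children. The values of *u* are assumptions.

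| u | N = 40 | N = 120 |
|---|---|---|
| 0 | 0 points | 0 points |
| 1 | 1/40 = 2.5 points | 1/120 = 0.8 points |
| 3 | 3/40 = 7.5 points | 3/120 = 2.5 points |
| 6 | 6/40 = 15.0 points | 6/120 = 5.0 points |

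For example, with r = 2 and N = 40, the rate is 2/40 = 5% on possible or probable. Under the SAP rule it is 5% if u = 0, 5/40 = 12.5% if u = 3, and 8/40 = 20% if u = 6.

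**Step 5: display threshold.** With one event per child, 4 possible or probable events plus 1 *unlikely* event make 5, and a listing becomes a table. This changes the format only.

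**The case against.** The strongest reply is that the SAP contradicts no protocol rule. The protocol sets no grade cut-off for related, device-related or ADE. It also separates the two lowest grades: *unrelated* needs causality to be definitively excluded, while *unlikely* does not. Counting everything not excluded is a coherent, cautious line. It resembles other SAP safety conventions, under which missing severity becomes severe, a missing relationship becomes related, and an AE that cannot be classified becomes treatment-emergent.

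Much of this stands. The analogy is incomplete, though. Those conventions deal with missing or indeterminate data, whereas an *unlikely* grade is neither. A cautious intent is possible, but the SAP does not state one.

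Three stronger readings are tempting, and the documents do not support them:

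- **That the SAP breaks the protocol's ADE definition, or leaves a required entry out of SAP 4.3.** With no cut-off in the protocol there is no explicit rule to break, and the absence from SAP 4.3 is not clearly an omission.
- **That the device-related rate is definitely overstated, for example 20% instead of 5%.** This needs at least one *unlikely* TEAE, and any such figures come from assumed counts.
- **That the main device-safety result is compromised and a skin signal could be hidden.** The SAP safety objectives (3.4) cover all AEs, TEAEs, SAEs and device incidents, and do not single out device-related TEAEs. The related summary is by SOC and PT, so rash terms keep their own rows. All TEAEs are also tabulated (16.1.1), and individual data are listed.

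**Conclusion.** The point holds as an inconsistency between the SAP's definition of related and the protocol's definition of the *unlikely* grade. Followed as written, the SAP reports as device-related any TEAE that the investigator graded improbable with another documented cause. The count is then higher than the possible-or-probable count and may differ from the ADEs that sites report under Protocol 7.3.

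The direction is certain; the size is not. The range of 0 to 15 points (N = 40) or 0 to 5 points (N = 120) rests on an assumed 0 to 6 children whose highest grade is *unlikely*. If there are none, recorded grades give the same count under either definition. The effect is on a descriptive safety summary, mainly its overall related total. The primary and secondary endpoints are untouched. Severity: minor.

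**What to change.** In SAP 16.1.1.2, define a device-related TEAE as one graded *possible* or *probable*, using the protocol's grade names. Beside it, tabulate TEAEs by all four relationship grades, so that *unlikely* events stay visible. If the wider set of everything not definitively excluded is kept, label it as a conservative sensitivity display and give the reason for it.

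The cost is one SAP sentence, one derivation flag and one added display. The downside is a less conservative headline count, which the four-grade table offsets. Because the protocol itself gives no cut-off, the change brings the table closer to the likely ADE reports but does not guarantee that the two agree.

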# **4.4.2.** Provision of Study Treatment

DryNites®, defined as the study treatment, is commercially available medical device of Class I and will be provided free of charge to the study participants. DryNites® should be used in accordance to this clinical investigation plan instructions. Study treatment and absorbent bed mats will be supplied to the participants by the Investigator/site; however, the use of bed mats is optional. A 4-week supply will be distributed to each participant's parents/carers at each visit Day 0, Day  $28 \pm 7$  days, and Day  $56 \pm 7$  days. In case of remote visits, study materials will be shipped by the site to the patient's address according to local law and regulatory instructions. All packages will be labelled "for use in clinical investigation only" (in the applicable local languages).

The younger age group will be provided with the 4–7 years DryNites® size. Parents/carers in the older age group will select whether age 4–7 or age 8–15 DryNites® size is most appropriate. DryNites® age 4–7 years are provided in packs of 10. As such, each participant will be provided with 4 packs of DryNites® to cover each 4-week period.

DryNites® age 8–15 years are provided in packs of 13. As such, each participant will be provided with 3 packs of DryNites® to cover each 4-week period.

Absorbent bed mats are provided in packs of 12. Each participant randomised in the intervention group (discontinuation of DryNites® pants) will be provided with 3 packs of bed mats to cover each 4-week period. Participants randomised in the control group (continuation of DryNites® pants) will receive 1 pack of bed mats per 4-week period. The use of bed mats is optional.

Any surplus of DryNites® and absorbent bed mats at the end of each 4-week period can be kept by the participant.

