## 7.2. Procedures for Reporting Adverse Events in the Case Report Form

All AEs (serious and non-serious) reported during the study period (from signature of the ICF until study discontinuation) will be captured on the appropriate study CRF.

Each suspected AE occurring during the study must be recorded in the appropriate CRFs and/or specific AE forms as designated by the Sponsor, including the description, seriousness criteria, severity, duration (onset and resolution date), causal relationship with the study device, actions taken with the study device any other required treatment, and outcome.

The following variables will be collected for each AE:

- AE (verbatim)
- Start and stop dates
- Event severity
- Seriousness
- Relationship with the study device
- Action taken with regard to the study device
- Outcome of the AE
- AE caused patient's withdrawal from study (yes or no)

In addition, the following variables will be collected for SAEs:

- Date AE met criteria for SAE
- Date Investigator became aware of SAE
- Criteria for seriousness
- If relevant: date of hospital admission and discharge
- If relevant: date and probable cause of death

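### The SAP counts a missing device relationship as related, with no exception for discontinuation-arm events to which the protocol says the assessment does not apply

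*SAP*

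**What the plan says.** **SAP.** Section 16.1.1.2 lists four relationship values: unrelated, unlikely, possibly and probably. There is no value for an assessment that does not apply. The section then states that "TEAEs with a missing relationship will be regarded as related". No arm or study period is exempted. Related events are to be tabulated by system organ class and preferred term, or only listed if there are fewer than five.

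**Protocol.** Section 7.1.5 says relationship "should be assessed for any AE occurring during the runin period and the intervention and extension periods in the control group", and adds that "it is not applicable for the intervention group". Section 4.4.2 confirms that the intervention group is the arm that discontinues DryNites. Section 7.2 includes "relationship with the study device" among the items recorded for an adverse event, without distinguishing arms and without giving a code for 'not applicable'.

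**Departures from protocol.** SAP section 4.3 records changes to the concomitant medication summary, the safety set and the definition of a treatment-emergent event. It does not mention relationship.

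**The concern.** Treating a missing relationship as related is a sound convention when an assessment was due and was omitted. It is not sound when the protocol says no assessment applies, because the blank then carries no information about causality.

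The protocol exempts one randomised arm, so the effect differs by arm. A continuation-arm event counts as device-related only after passing through investigator judgement (or a true omission). A discontinuation-arm event with a blank field counts automatically, and with 2:1 allocation that is the larger arm. Protocol section 2 says the side-effects of DryNites have not been evaluated in any study, so the by-group summary of device-related events will be read with interest. Some of what it attributes to the device could come from children assigned not to wear it.

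**Working it through.** The documents contain no adverse event rate and no related-event figure to reproduce. The check is a comparison of texts, followed by an illustration on stated assumptions.

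**1. The two rules side by side**

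| Adverse event | Protocol 7.1.5 | SAP 16.1.1.2 if the field is blank |
|---|---|---|
| Run-in, any child | Assess | Related |
| After randomisation, continuation arm | Assess | Related |
| After randomisation, discontinuation arm | Not applicable | Related |

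The first two rows are the usual conservative handling of an omission. The third is the conflict.

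**2. Do the third-row events reach the table?** Yes.
- SAP 6.3: the safety set is everyone who used DryNites for at least one night after consent. All children are assigned DryNites in run-in, so the discontinuation arm is included.
- SAP 16.1: the treatment-emergent window runs from the start of screening to the end of the extension, so post-randomisation events qualify.
- SAP 16.1 and protocol 5.4.4: device-related events are tabulated for each group.

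**3. Illustrative count.** Protocol 4.3 aims to randomise about 120, and 4.3.5 allocates 2:1, so 120 × 2/3 = 80 discontinue and 40 continue. Let *p* be the share of children with a post-randomisation adverse event (assumed). Assume every discontinuation-arm field is blank and each affected child has one event. Mislabelled children = 80 × *p*. The chance of at least five is the binomial tail with n = 80.

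| *p* (assumed) | Mislabelled, of 80 | Chance of 5 or more |
|---|---|---|
| 5% | 4 | 0.37 |
| 10% | 8 | 0.91 |
| 20% | 16 | about 1.00 |
| 30% | 24 | about 1.00 |

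Below five related events in total there would be a listing instead of a table, with the same label. The figure of 80 is the upper end. Protocol 5.2 needs 45 per age group at randomisation and adds 15 for both dropouts and run-in exclusions. If all 15 per age group were lost before randomisation, 90 would be randomised, 90 × 2/3 = 60 would discontinue, and the range would be 60 × 5% = 3 to 60 × 30% = 18.

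**4. Between-arm contrast.** Let *f* be the share of assessed events classed as related (assumed), with the same *p* in both arms.
- Post-randomisation events only: *p* against *pf*, a ratio of 1/*f*.
- With run-in events added at the same *p*: *p*(1 + *f*) against 2*pf*, a ratio of (1 + *f*)/(2*f*).
- Mislabelled events as a share of all related events over run-in and intervention: 80/(80 + 160*f*), since on-device child-periods number 120 + 40 = 160.

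| *f* (assumed) | Ratio, post-randomisation | Ratio with run-in | Mislabelled share |
|---|---|---|---|
| 0.10 | 10 | 5.5 | 83% |
| 0.25 | 4 | 2.5 | 67% |
| 0.50 | 2 | 1.5 | 50% |

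Above *f* = 0.5 the mislabelled events are no longer the majority. If every child also entered the extension, the break-even would be 160 = 200*f*, so *f* = 0.8. If the continuation arm has a different incidence *q*, the discontinuation arm shows the higher rate only when *p* exceeds *fq*.

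**5. After correction.** With 'not applicable' kept apart from missing, the rule makes 0 of 80 children device-related. Run-in events in those children keep their assessed relationship.

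**The case against.** The strongest reply is that 'not applicable' is not the same as missing. The documents never say sites will leave the field empty. Protocol 7.2 lists relationship for each event, protocol 6.5 promises programmed checks for missing data, and the eCRF is not supplied. Sites might enter 'unrelated', or the form might carry a 'not applicable' code, and then the missing rule need not operate. This stands: a reader might infer that the field is blank by design, but that is an inference from 7.1.5 and the point has to be conditional. It does not remove the gap, because a 'not applicable' code would have no defined handling in the SAP either.

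A reader might also infer that most device-related events would fall in children not wearing the device, or that the safety comparison would be reversed. The documents do not support either. The table also takes in run-in events, when every child is on DryNites, and both results turn on *p*, *q* and *f*, none of which is given. A high *f* is plausible, because the SAP leaves only 'unrelated' outside the related group and the protocol reserves that term for events where causation can be definitively excluded. SAP 8.1 plans no confirmatory testing, and SAP 7 lists individual data, so the mislabelling could be traced.

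The same SAP section counts 'unlikely' as related. That is a pre-specified conservative choice applied alike to both arms, and no objection is made to it.

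Lastly, the SAP was written against version 1.0 of the clinical investigation plan and the protocol supplied is version 3.0. The Amendment 2 log lists no change to 7.1.5, but the version 1.0 text cannot be checked.

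**Conclusion.** The conflict is real and unresolved. Followed together, the two documents leave post-randomisation discontinuation-arm events either coded as device-related (if the field is blank) or without defined handling (if it holds a 'not applicable' code). In the first case that arm's device-related count is inflated by every such event.

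The mechanism follows from the texts; the size does not. The range of 4 to 24 children rests on 80 in the arm, an assumed 5% to 30% incidence, one event per child and every field blank. With 60 in the arm it is 3 to 18. The between-arm ratios of 1.5 to 5.5 with run-in events included further assume equal incidence and 10% to 50% of assessed events classed as related. Run-in events in the same children are not affected, and neither is the primary endpoint. The point should be corrected because it can give a wrong classification in a planned safety output and is cheap to close.

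**What to change.** In SAP 16.1.1.2:

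- Add a 'not applicable' category for adverse events with onset after randomisation in the discontinuation arm where no relationship was recorded, and show it separately from 'related'.
- Apply the missing-means-related rule only to events for which protocol 7.1.5 requires an assessment: run-in for all participants, and the intervention and extension periods in the continuation arm.
- Keep and tabulate any relationship an investigator does record in the discontinuation arm. Protocol 4.3.8 anticipates some use of pants there, so a blanket exclusion could hide a real device effect.
- Keep all these events in the all-TEAE tables.
- State on which side of the line an event starting on the day of randomisation falls. SAP 7.2 treats it as post-baseline, although the child has just finished four weeks on DryNites.

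Before programming, check how the eCRF stores relationship for this arm, and record the clarification in SAP 4.3. The cost is a few lines of SAP text and one flag built from arm and onset date. Data collection, trial conduct and clinical care do not change.
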